We will collaborate closely with other RADx-UP projects to share data and adapt processes and continuously communicate with our community partners to assess effectiveness and disseminate research findings. Quantitative approaches will include measurements of provider-level, care process, community-level, and patient-level outcomes. Qualitative approaches will include capturing information via semi-structured interviews, exit surveys, and in-depth program implementation process observations. The goals of the evaluation are to: (1) identify community facilitators and barriers to testing; (2) monitor ethical and social implications of testing; (3) measure the fidelity of the practice implementation support strategy; (4) determine the effectiveness, acceptability, and reach of the implementation support model for disseminating and helping practices to implement SARS-CoV-2 testing protocols; and (5) determine the effectiveness of different testing modalities.

E. Chart Review

1. For those practices that cannot generate performance measure data from the EHR, we will provide a chart abstraction protocol for obtaining performance measures through manual chart abstraction of the practice EHR.
2. More specifically, we will be collecting structured data needed for calculating performance measure from automated measure reports built into the EHR, or where these are not available, but developing a Registry Report to collect the data needed to calculate the performance measures.
3. Only aggregated performance measure data (therefore, deidentified) will be entered into REDCap.

4. Entry of data into REDCap will have user controls and logged access.
5. At the end of the Project, the data will be stored for potential future analysis for 10 years.

F. Biospecimens

No specimens will be obtained from participants except for the limited serology studies performed with our collaborators at the Oklahoma Medical Research Foundation, and only for those with positive POC test results to allow confirmation on other platforms. Participants in the limited serology study will be fully consented to participate in the research study. For all other participants, the only research material will be the data obtained by surveys, direct observation, key informant interviews, and medical record abstraction. Abstractions will be conducted at the practices.

G. Banking/Repository/Database

Information pertaining to COVID-19 screening, testing, and treatment will become part of the practice's standard medical record and will not be available to third parties other than the study team under OUHSC IRB protocol. Information from medical record abstractions will be immediately de-identified and coded on site by a trained abstractor. De-identification of patient records means that all patient identifiers listed in HIPAA regulations including, but not limited to, name, date of birth, social security number, medical record number, insurance identifiers, address, zip code, phone number, and email address will be removed so that research data cannot be linked directly to individual patient records without participant codes. Each participating practice, clinician, and patient will be assigned a code number matched to an identifier. A list that links the code number with the patient's name and medical record number will be kept in a secure location by the data analytics team.

Note, identifiers might be removed and the de-identified information may be used for future research without additional informed consent from the subject.

H. Inclusion / Exclusion Criteria

Inclusion Criteria:

Practices

1. Primary care practices located in Oklahoma.
2. Priority to practices serving a majority of patients that are underserved or vulnerable populations (rural, minority, elderly).
3. Practices routinely using a certified electronic health record (EHR) will be eligible to participate, as practices that are still using paper records are either planning to close due to clinician retirement or will likely be implementing an EHR during the project, which would compromise their ability to participate.
4. Practice-wide participation will be encouraged, but participation of all members within a practice (both clinicians and staff members) will not be required. The minimum acceptable level of participation will be one clinician and nurse/medical assistant dyad plus anyone else who would have to be involved to make changes in the processes of care (e.g. clinic manager) for that unit of care.
5. Clinicians and staff members 18 years of age and older at the time of enrollment (consent).

Patient Survey Participants

1. Patients (or caregivers of patients) who are seen in eligible practices or community testing sites and received a recommendation for the patient to receive a SARS-CoV-2 diagnostic test.
2. Patients (or their caregivers) who are 18 or older.

Exclusion Criteria:

Practices

1. Practices that are uninterested in reducing missed opportunities for guidelines-based testing for SARS-CoV-2
2. Solo practices with a clinician planning to retire within 12 months of enrollment will not be eligible for participation.
3. Practices likely to experience ownership change in the next 12 months will not be eligible for participation.

Patient Survey Participants

1. Patients unable to complete the consent process or survey instruments in English.
2. Patients or caregivers of patients who are under the age of 18.

Early Termination Criteria:

1. **Practices:** Deny access to data needed to calculate performance measures. Decline to participate with Academic Detailers or Practice Facilitators in the practice change interventions.
2. **Clinicians:** Inability to participate with the external support provided to the practice. Terminates relationship with the practice.
3. **Staff:** Terminates employment with the practice.
4. **Patients:** Decline to participate. No longer with the primary care practices enrolled in the CATCH-UP Project.

I. Gender/Minority/Pediatric Inclusion for Research

No clinicians or staff members will be excluded from participation based on gender, ethnicity, race, or socioeconomic status. For the Provider and Practice Surveys, no provisions for including non-English speakers or those with limited fluency in English have been made due to the resources needed to develop multilingual materials and processes. Women clinicians and staff members may be pregnant, planning pregnancy, or breastfeeding during the course of this study and therefore will be eligible to participate.

No patients will be excluded from this study due to gender, ethnicity, race, or socioeconomic status. The study design involves targeting practices and communities that tend to be more rural or primarily serve underrepresented populations.

English-language only status would not be a limitation to being tested as part of this study. While there are limitations to the generation of surveys in other languages, every provision possible will be made to include Spanish-language materials and surveys to ensure the ability of Spanish-only speakers to participate in this study.

J. Recruitment and Enrollment

We will enroll 50 practices, which is approximately 3% of the primary care practices in Oklahoma. Practices will be defined as clinician-staff units that work together to deliver care to a population of patients. These care units may be a 'pod' or 'clinic' within a larger health system with multiple practices located at the same street address of a medical building. The practice, or microsystem, has the responsibility and capacity to implement Quality Improvement (QI) interventions with or without corporate or larger group assistance. We will prioritize small- and medium-size primary care practices (<10 clinicians) to participate in this project. A practice facilitator (PF) will contact interested practices to screen for eligibility and arrange a date for enrollment, if applicable. During in-person enrollment, participating clinicians and office staff will receive additional information and be able to ask questions and express concerns about the project. Those still interested will sign an informed consent document and a lead clinician and participating staff will complete baseline surveys.

Patients undergoing SARS-CoV-2 testing will be given a card/flyer with information about participating in surveys about attitudes towards COVID-19 and barriers and facilitators of testing. Consent for low-risk survey participation will occur through a REDCap form. We do not plan repeated survey measures and thus retention is not applicable.

K. Risks and Benefits

Our study focuses on the translation of evidence-based guidelines into practice. The major risk to the clinicians and office staff is loss of productivity and income. It will take some time to complete enrollment forms and questionnaires and help the practice facilitators and medical record abstractors access the performance data. In addition, the level of clinician and practice performance will be known to the research team, which if below average, might make practices' staff feel uncomfortable. The risks to patients are minimal. They involve risks associated with abstraction of their records (confidentiality) and temporary disruptions in services associated with efforts to improve care processes. There may also be concerns of loss of confidentiality when completing the Patient Surveys.

For those participating in the limited serology study, it remains a minimal risk study, where possible risks associated with blood draws include: occasional slight discomfort associated with blood drawing and occasional hematoma (bruise) or infection at the blood drawing site. Rarely, a participant may experience fainting or dizziness.

Human Subjects Protection Training

All investigators and staff involved in this Project have undergone human subjects' protection training as specified by their individual organizations.

IRB Review and Oversight

The conduct of the Project will be periodically reviewed and overseen by the appropriate IRBs to ensure that human subjects are being adequately protected.

Quality Improvement Components – *Benefits for the Practice*

1. Feedback on performance at baseline and throughout the intervention period.
2. Benchmarking comparisons of performance to other clinicians/practices in the project.
3. Updates on latest evidence and guidelines.
4. Clinical Decision Support Tools (e.g. algorithms, one-pagers, summaries).

5. Insights from and opportunities to interact with high performing clinicians/practices.
6. Access to increased testing for their own staff and patient population.
7. A Practice Facilitator to assist with workflow redesign and quality improvement efforts.
8. Assistance developing and implementing electronically-generated quality reports in practice workflow.
9. Opportunities to contribute to communitywide healthcare improvement initiatives.

Quality Improvement Components: *Benefits for Patients*

1. Improved access to decision support resources for COVID-19 screening, testing, and treatment.
2. Potentially better health outcomes.
3. Increased participation in decision-making regarding their health.

Project Evaluation (Research Component) Benefits

1. If the project is successful, it will improve the probability of future funding for similar types of assistance in the future.
2. Development of electronic data capture and reporting in EHRs will help clinicians/practices and health systems with continuous quality improvement.

L. Multiple Sites

Not applicable.

M. Statistical Methods

Descriptive statistics and qualitative summaries will be reported to summarize implementation process measures (type, dose, frequency, and sequencing of provided support strategies) and the facilitators and barriers of implementation.

We will calculate descriptive statistics for all Aim 1 measures and will perform formal hypothesis testing to compare pre- versus post-implementation provider- level, care process, and patient- level outcomes at the patient and practice levels. In addition to this pre-post analysis, trends in testing rates will be explored. A mixed effects linear regression model will be fit to explore changes in testing rates over time relative to the control period (0 months on intervention), accounting for correlation among repeated measures on the same practice and among practices nested within PFs will be accounted for using random effects.³⁸

Descriptive statistics and qualitative summaries will be reported to summarize the facilitators and barriers to implementation. We will calculate descriptive statistics for all Aim 2 measures. County-wide initiatives to amplify community- based testing that are initiated by CHIOs will be descriptively summarized as a function of county, region, and time period. Patient Survey data and program implementation process observations will be used to understand the influence of internal and external contextual factors on the success of community-based testing events. For qualitative data analyses, we will use software-assisted (NVIVO v12) content analytic techniques. Key informant interviews will be transcribed and evaluated by at least two independent coders. Initial codes will be compared across evaluators and emergent thematic categories will be argued to consensus and graphically represented for a better understanding of their meaning and relationships. Although much of the interviews will be guided by a solid understanding of well-known facilitators and barriers to testing, we will be intentionally open to new or unexpected qualitative findings. A subset of the transcripts (10%) will be chosen at random and coded by another researcher to achieve an inter-rater reliability kappa of at least 90%.³⁹⁻⁴⁰ Disagreements on codes will be resolved by discussion. We will take steps to minimize

potential bias⁴¹ including conducting regular debriefs with members of the evaluation team. To better understand perceptions of the utility, effectiveness, and generalizability of the CATCH-UP program, detailed PF implementation notes will be summarized and analyzed according to the domains of the program model.

N. Data and Safety Monitoring Plan

Please note that confidentiality of the data in this Project will be safeguarded in accordance with the General Policy for Security and Access of University of Oklahoma School of Community Medicine. OU IT has implemented mechanisms to protect the privacy and security of all university data. OU-Tulsa's computer network, file servers, and network storage arrays are secured through role-based access control restricting users' access based upon their roles and responsibilities to prevent unauthorized access. Servers and network storage arrays are also physically and virtually secured and routinely monitored and backed up. University work-stations and terminals are secured by requiring domain membership and user authentication by logging in with a unique user ID and password for access, and log off or lock-down their station if the individual is absent/idle for more than 10 minutes. Passwords must comply with OUHSC Password Security policy and procedures.

O. Data Sharing

We are confident that we can most effectively disseminate the methods, products, and results of this initiative within Oklahoma and nationally. This will occur through both formal and informal mechanisms. We commit to a rigorous collaboration with other RADx-UP sites through our Consortium Data Reporting Unit in order to ensure our interim findings are disseminated rapidly to benefit other projects. We agree to review and provide timely feedback to NIH staff regarding materials they produce about this project. We will also provide high- level quarterly reports on the progress of our project and program to NIH and CDCC, and we will share any products we develop (e.g. results, publications, tools, etc.) for inclusion in NIH initiative descriptions. Finally, we agree to share our methods, results, and products with NIH, and other awardees and make our data available through a Data Use Agreement with other interested researchers.

While meeting the formal definition of a clinical trial, it is a Dissemination and Implementation Research study to assist primary care practices to effectively implement established guidelines and best practices. The project PI and the Regulatory Coordinator will submit the study to ClinicalTrials.gov to determine if the study should be listed to meet Federal requirements. In the event this study will be required to be registered, we will complete registry prior to enrolling the first participating practice. Once a record is established, the PI and the leadership team will confirm accuracy of record content; resolve problems; and maintain records including content update and modifications. The PI and the leadership team will be responsible for aggregate results reporting at the conclusion of the project and AE reporting. All reporting and submission of results will occur within the timeframes in the NIH Policy on Dissemination of NIH-Funded Clinical Trial Information. Note, informed consent documents for this study will include a specific statement relating to posting of this trials information and results at ClinicalTrials.gov.

P. Confidentiality

Efforts will be made to keep practice, clinician, and staff personal information confidential. Participants will not be identifiable by name or description in any reports or publications about this Project. We cannot guarantee absolute confidentiality. Personal information may be disclosed if required by law. Data will be stored for a minimum of 10 years. No one outside of the research team will have access to the Project data. Survey data and performance measurement data will be entered into REDcap. Paper copies of surveys and signed consent forms will be stored in a research storage room in the OU-Tulsa Schusterman building behind two locks, a locked office door and a locked drawer.

Q. Literature Cited

1. Team CC-R. Geographic Differences in COVID-19 Cases, Deaths, and Incidence - United States, February 12-April 7, 2020. *MMWR Morb Mortal Wkly Rep.* 2020;69(15):465-71. Epub 2020/04/17. doi: 10.15585/mmwr.mm6915e4. PubMed PMID: 32298250.

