the beginning of the project. Subjects for this research project will include primary care clinicians and their office staff. They will be interviewed and observed, and their performance will be evaluated. Each practice will be asked to complete one approximately 15-minute Practice Characteristics Assessment twice (at enrollment and at the end of the study).

Each clinician and office staff member will be asked to complete a 10-minute Provider Survey at baseline and quarterly thereafter. The Practice Characteristics Assessment and Provider Surveys will be delivered to practice staff via an email that includes a web-based REDCap survey link. Medical record data will be abstracted from each practice for performance feedback and outcome measure assessment using EHR registry reports. Each practice will receive support from academic detailers and practice facilitators and performance reports to improve their processes of care.

Patients will be involved in two ways, through completion of patient surveys and through retrospective abstraction of their medical record data for performance tracking and reporting. Patients offered SARS-CoV-2 testing (at either a participating primary practice or mobile testing unit) will be provided a flyer that includes both a QR code and URL to the Patient Survey in REDCap. This survey will be completed anonymously and set up to ensure that patients can only complete the survey one time.

Key Informant Interviews (KII) and Patient/Provider Surveys

KII will be conducted over Zoom at the beginning and end of the project, with community stakeholder, provider, and patient representatives to help inform the facilitators and barriers to be included in the Practice/Provider and Patient Surveys with a focus on identifying and capturing those encountered by underserved, vulnerable populations. Participants will be consented electronically via REDCap prior to conducting the interviews. Provider and Patient Surveys responses will also be monitored on a monthly basis and shared with the SAB and CAB to identify whether adaptations to our program are needed.

Practice/Provider Surveys will be delivered to practice staff via an email that includes a web-based REDCap survey link. When offered testing, patients will be given a flyer with a QR code and web-based link to complete the Patient Survey via REDCap. The survey link will be unique for each flyer to ensure that an individual can only complete the survey once.

Testing Capacity

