Practice Facilitation: PF support will begin with an intensive phase of half-day in-practice or virtual visits weekly for 3 months and follow with a maintenance phase of monthly visits for 6 months or more frequently if new POC technologies are deployed. Using a suggested support plan for each visit, the PF will help the practice form a QI team and engage clinical leadership in implementing the CATCH-UP testing protocol. The PF will document the support plan, support provided, and the outcome achieved by the practice in the OPHIC Electronic Practice Record (EPR), a system we developed to document all interactions with a practice, goals and accomplishments for facilitation encounters, and plans for the next contact. The structured notes in the EPR will guide facilitation planning indicating the anticipated services that will be provided during a visit as well as what happened during the visit and the practice's responsiveness and engagement in the improvement activity. EPR notes permit other PFs to fill in without interrupting the support plan and provides a record for analysis needed to improve the facilitation process itself.

Information Technology Support:

The PF, with the assistance of Oklahoma Foundation for Medical Quality (OFMQ) will help maximize the EHR's documentation and reporting capacity to capture testing process data. They will train clinicians and staff in the proper use of the EHR and introduce tools such as a care management registry to assure a seamless incorporation of SARS-CoV-2 testing into the existing workflow (including the use of POC technologies when implemented), consistent documentation, performance measure reporting needed to stimulate and track data- based improvement, and integration into the OSDH data reporting system for surveillance and contact tracing.

In addition, OFMQ collaborators will provide support for chart abstraction protocols, development of novel measures, quality control, and training of OPHIC PFs. They will provide technical advisors for both practice-based and community- based testing to participate in the generation of performance measures, assist with EHR data extraction and integration of POC diagnostic equipment, and visit practices as needed to facilitate more effective EHR use.

Virtual Learning Community is created by clinician and staff engagement in RPR Exchange.³³ The RPR Exchange creates a learning community by providing: (1) e-mail or text messages

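### For the EHR-derived Aim 1 care-process measures, an uncontrolled pre-post change in testing rate can partly reflect changed recording, because the intervention alters the EHR from which the outcome is read

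*Protocol*

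**What the plan says.** **The intervention.** Under Information Technology Support (Protocol section D), practice facilitators, with the state quality organisation, are to make the most of the EHR's "documentation and reporting capacity to capture testing process data". The same paragraph continues: "They will train clinicians and staff in the proper use of the EHR".

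**The outcome source.** The opening of Protocol section D states: "Medical record data will be abstracted from each practice for performance feedback and outcome measure assessment using EHR registry reports".

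**The extraction method.** Section E (Chart Review) allows three routes. Item 2 takes data "from automated measure reports built into the EHR, or where these are not available, but developing a Registry Report". Item 1 adds a manual route: "For those practices that cannot generate performance measure data from the EHR, we will provide a chart abstraction protocol". Section K, item 8 of the benefits for the practice, offers "Assistance developing and implementing electronically-generated quality reports in practice workflow".

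**The analysis.** Protocol section M and the SAP's Statistical Methods carry the same text. The investigators "will perform formal hypothesis testing to compare pre- versus post-implementation" outcomes, including care-process outcomes. They also fit an exploratory mixed linear model of testing rates whose reference is each practice's time at zero months on intervention. Aim 3 lists testing, positivity and refusal rates among the care-process outcomes without defining a numerator or denominator.

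**The concern.** Between the pre and post windows, the intervention works on the instrument that measures its own effect. If tests are recorded more completely after facilitation, the measured rate rises even when no more tests are done. If the way data are pulled from the record also changes, the two windows are not measured alike.

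Nothing in the planned analysis separates more testing from better recording. The random effects for practice and facilitator describe correlation; they do not correct a measurement shift that coincides with the intervention. A larger sample estimates the biased quantity more precisely. At stake is the evaluation goal in section D (Program Evaluation and Dissemination) of judging whether the implementation support model is effective.

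**Working it through.** The documents give no capture rate, baseline testing rate, effect size, alpha or power, so there is no planned figure to reproduce. What follows is illustrative, and every capture share and SD is an assumption.

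**1. How capture enters the rate.** Let r be the share of tests done that are entered in the record, m the share of recorded tests that the extraction method finds, and s = r × m. Let d be the share of the true denominator that is counted. With no true change in testing:

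observed post/pre ratio = (s1/s0) ÷ (d1/d0)

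**2. Numerator only (d unchanged).**

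| Assumed s0 | Assumed s1 | Ratio s1/s0 |
|---|---|---|
| 0.90 | 0.95 | 0.95/0.90 = 1.06 |
| 0.80 | 0.95 | 0.95/0.80 = 1.19 |
| 0.70 | 0.95 | 0.95/0.70 = 1.36 |
| 0.50 | 0.95 | 0.95/0.50 = 1.90 |

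**3. Cases that go the other way.**
- A switch from thorough manual abstraction to a report that finds less, 0.95 to 0.85: 0.85/0.95 = 0.89.
- Denominator recording improves as much as numerator recording, both 0.80 to 0.95: 1.19 ÷ 1.19 = 1.00.
- Denominator recording improves more, 0.60 to 0.95, against a numerator of 0.80 to 0.95: (0.95/0.80) ÷ (0.95/0.60) = 0.60/0.80 = 0.75.
- Positivity: if positive and negative tests are captured equally well, the shift cancels.

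**4. Could it produce a significant result alone?** Section J gives 50 practices. Take a paired t-test on log rates, two-sided 0.05, with an assumed SD of 0.5 for the within-practice change in log rate. The standard error is 0.5/√50 = 0.0707, and the noncentrality is ln(ratio)/0.0707.
- 0.90 to 0.95: 0.0541/0.0707 = 0.76; probability of significance 12%.
- 0.80 to 0.95: 0.1719/0.0707 = 2.43; probability 66%.
- 0.70 to 0.95: 0.3054/0.0707 = 4.32; probability 99%.

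For 0.80 to 0.95 the probability ranges from 98% (SD 0.3) to 32% (SD 0.8). With unchanged capture it is 5%.

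**5. What the documents offer against it.** Information Technology Support mentions quality control and help with abstraction protocols, but gives them no content. Neither document holds the method fixed within a practice, re-extracts baseline, compares capture between periods or plans a sensitivity analysis on this point.

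**The case against.** Three points on the other side have force.

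**Baseline capture may already be high.** Eligible practices must routinely use a certified EHR (section H), and testing is expected to start through existing laboratory relationships (section D, Testing Capacity). That makes the 1.06 case at least as plausible as 1.36 or 1.90. This stands: the documents do not favour any one row of the table.

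**The switch of method is not stated.** A reader might infer that practices starting with manual abstraction will be moved to electronic reports. Section E assigns the route by what a practice can produce, and item 8 in section K is a general benefit not tied to manual-abstraction practices. A within-practice switch is permitted and foreseeable, but not planned in terms.

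**The direction is not fixed.** A reader might also infer that the bias always favours the intervention. That holds for better documentation of tests in the numerator. It does not hold for a method switch, nor for an undefined denominator that may itself be better recorded once the standardised patient screening described in section D is in place.

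The trend model is labelled exploratory, but the pre-post comparison is described as formal testing, so that label does not dispose of the point. Unspecified quality control does not answer it either.

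**Conclusion.** The point holds for the EHR-derived Aim 1 care-process measures and no further; survey outcomes and mobile-unit test counts do not depend on this mechanism. A pre-post change in testing rate can partly reflect differential capture, and the plan has no means of telling how much.

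It would be too strong to say that a rise would be nothing but documentation gain. The documents give no capture rate, so they support neither that reading nor any particular size. The ratios of 1.06 to 1.90 rest on assumed capture shares, a numerator-only shift and no true change. The significance probabilities rest further on an assumed test, alpha and SD. The upward direction applies only to better documentation of tests. The documentation part of the mechanism is explicit in the protocol; the method-change part is an inference from what sections E and K allow.

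**What to change.** In the SAP:

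1. Define one numerator and one denominator for each care-process rate, and one extraction method per practice, and apply them to both the pre and post windows.
2. If a practice's method changes, record the date and re-run the new method over the baseline window before making the comparison. The protocol's retrospective abstraction makes this possible.
3. Count tests from all orders and results in the record, including outside-laboratory and in-practice point-of-care results, not from newly introduced structured fields. This must accompany step 2: a report reading only new fields would find too little at baseline, and a laboratory-only count could miss in-practice tests later.
4. Add a sensitivity analysis limited to practices whose extraction method did not change.
5. State in the SAP that residual documentation gain cannot be excluded. Steps 1 and 2 address the method (m); step 3 reduces dependence on new documentation habits, but r can still differ between windows.

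Two other remedies may suggest themselves but are not recommended. A time-varying indicator for documentation change would be close to collinear with time on intervention and could absorb true effect. A subset of practices with no documentation change may be empty, since documentation support is part of the general model.

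**Cost.** Some re-extraction at the practices, because section E sends only aggregates to REDCap. Tests or refusals never recorded at baseline cannot be recovered.
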